## **Bias considerations**

The minimization of biases and confounding are major tasks when conducting a cohort study. By the nature of this type of study, randomization cannot be introduced to minimize these. Therefore, in the patient selection, major efforts have to be taken to minimize any type of bias. Special care has to be taken with regard to selection bias, i.e. the selection process to decide whether a patient is eligible for the study entry.

In order to minimize selection bias and treatment bias over time across the centers, we plan to select the 2,200 consecutive cases from GCMR registry using a search criteria of stress CMR studies performed between 2008-2012. We plan to restrict the contribution from each of the sites to between 100-500 consecutive studies. Unsuccessful cases (technical failures or patient factors) during the same time interval will also be recorded for the purpose of a separate analysis of study success rate.

A large selection of possible confounders will be collected to assess any differences between the two groups of patients (patients with and without ischemia) to assess any differences between the groups with regard to e.g. medical history, demographics and baseline characteristics.

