### Study Cohort and Enrollment Criteria

Consecutive patients who underwent stress CMR perfusion imaging for evaluation of myocardial ischemia between 2008-2013.

**Inclusion Criteria:** all of the following at time of imaging:

- a) male or female at age 35-85 years,
- b) presence of either of the following sign/symptom that led to stress CMR imaging
  - 1) Symptoms suspicious of ischemia, or
  - 2) abnormal ECG with a suspicion of coronary artery disease
- c) Intermediate or high risk of significant coronary disease based on at least 2 of the following conditions:
  - a. patient age > 50 for male, 60 for female
  - b. Diabetes: by either history or medical treatment
  - c. Hypertension: by either history or medical treatment
  - d. Hypercholesterolemia: by either history or medical treatment
  - e. family history of premature coronary disease: first degree relative at age <= 55 male and <=65 female
  - f. Body mass index > 30
  - g. Any medical documentation of peripheral artery disease
  - h. Any history of myocardial infarction or percutaneous coronary intervention

**Exclusion Criteria:** any of the following at time of imaging:

- a) Prior history of coronary artery bypass surgery (CABG)
- b) Acute myocardial infarction within the past 30 days prior to CMR
- c) any significant non-coronary cardiac conditions confirmed by medical documentation
  - a. severe valvular heart disease,
  - b. non-ischemic cardiomyopathy with LVEF <40%,
  - c. infiltrative cardiomyopathy,
  - d. hypertrophic cardiomyopathy,
  - e. pericardial disease with significant constriction, or
- d) active pregnancy,
- e) any competing conditions leading to an expected survival of < 2 years
- f) Known inability to follow-up due to logistical reasons (e.g. patient lives in another country where follow-up is not feasible)

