## Number of Sites

It is expected that a range of 6-15 US centers will participate. Each site will be screened by a sample survey and is required to provide a limited dataset to verify the existence of the stress CMR studies, completeness of key pulse sequences (cardiac function, stress perfusion, and LGE imaging), and diagnostic quality for ischemia assessment. To qualify for the study, a site needs to demonstrate:

- a) Willingness/ability to provide a screening dataset
- b) Can contribute at least 100 studies
- c) <10% of the consecutive cohort were deemed diagnostic inadequate by the site

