**Step 1: Propensity Score to Treatment** We plan to structure the study analysis of observational data in SA1 to mimic a randomized clinical trial: a) assignment of coronary intervention (INT) vs. medical therapy (MED) is based on the therapy selected in the initial 60 days after imaging and b) nonrandomized treatment adjusted for via a propensity score. Either PCI or CABG will define coronary revascularization. Follow-up time begins at the time of the index stress CMR imaging. To adjust for non-randomization of treatment, a single propensity score will be developed using logistic regression to model the decision to refer to revascularization considering all factors known to influence the referral decision. This single composite propensity score represents the probability of treatment assignment, which will be included in all subsequent survival models (step 2) associating stress CMR perfusion guided-treatment with the respective endpoints in each of the 3 sub-aims. This adjustment reduces the bias introduced by nonrandomized referral to INT in practice. While all factors known to influence this referral decision will be considered for entry into this logistic regression model, based on existing literature, the most likely predictors of referral to INT include % ischemic myocardium (% myocardial mass based on number of segments, by CMR), typical angina symptoms (yes if positive response to 2 of 3 Diamond and Forrester qualities, else no), infarct size (LGE size, grams of myocardial mass), ischemic ST changes on rest ECG (yes/no), pre-test coronary disease probability (ordinal), and prior cardiac catheterization (yes/no). We anticipate that 10-15% of patients (~n=300) received INT so model over-fitting will not occur when constructing this logistic regression model.

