**Step 2: Multivariable survival analyses for treatment's impact incorporating the propensity score (sub-aims 2.1 and 2.2).** A Cox proportional hazards model will be used to assess the association of treatment with the primary outcome (sub-aim 2.1) and secondary outcome-free survival (sub-aim 2.2). For each of sub-aim 2.1 and 2.2, we plan to build a survival model using Cox proportional hazards regression to control for the effects of baseline patient differences. Key known risk markers to be included in these models are age, sex, diabetes, and % ischemic myocardium. Major Treatment (INT or MED) and the propensity score will then be entered into the model to assess for any survival advantage from INT vs MED adjusting for the nonrandomized referral pattern. Any potential impact by any covariate in the model onto the survival benefit from INT, will be tested by adding an interaction term between treatment and the covariate of interest.

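### Site and scan year are named in no Cox or propensity model, although the plan itself raises treatment bias over time and across centers

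*Combined protocol and SAP*

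**What the plan says.** On sites, Number of Sites states: "It is expected that a range of 6-15 US centers will participate". Bias considerations limits each site's share ("restrict the contribution from each of the sites to between 100-500 consecutive studies") and gives the purpose: "In order to minimize selection bias and treatment bias over time across the centers". The measures listed there are consecutive selection, a date window and the per-site limits.

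On the models:

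- **Aim 1** (Specific Aim 1, and Statistical Analyses, Specific aim 1). Age, sex, LV volume, pretest probability and the Diamond-Forrester score are given as examples of covariates. Ischemia is then added.
- **Propensity score** (Specific aim 2, Step 1). Any factor believed to drive referral may be considered. The text then says "the most likely predictors of referral to INT include % ischemic myocardium" and lists five more: typical angina, infarct size, ST changes, pretest probability and prior catheterization. All six describe the patient.
- **Aim 2 Cox models** (Step 2). "Key known risk markers to be included in these models are age, sex, diabetes, and % ischemic myocardium". Treatment and the propensity score are then entered.

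Site and scan year appear in none of these in any role.

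The CMR Imaging part of Data to Collect takes ischemia extent from site reports. Core Lab DICOM Reads covers a 10% sample, for image quality, and is not meant to challenge the site's reading.

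**The concern.** Consecutive sampling guards against hand-picking within a site, and the cap limits any one site's weight. Neither makes sites alike in how readily they revascularize, whom they scan or how they read perfusion. The Background describes a registry spanning academic, community and private practice, so differences are to be expected.

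For sub-aims 2.1 and 2.2, a site with a high INT rate and an unusual event rate, for reasons the patient-level covariates miss, confounds INT against MED. The error can go either way, including towards a false INT benefit, which is what these sub-aims test for. Scan year can act in the same way. A cap on consecutive studies may also make high- and low-volume sites cover different years.

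A second, smaller issue is that annualized event rates pooled over sites get intervals that are too narrow if patients within a site are treated as independent.

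**Working it through.** **1. The plan's own figure.** Sample Size gives a detectable HR of 0.59 with 80% power, two-sided 5% and a 77:23 split. Schoenfeld: events = (1.960 + 0.842)² / [0.77 × 0.23 × (ln 0.59)²] = 7.849 / (0.1771 × 0.2784) = 159.2, so 160. This matches the group counts 124 + 36 = 160 (power 80.2%). The listed total of 150 gives 77.6%.

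**2. Scale.** 2,200/15 = 147 and 2,200/6 = 367 patients per site on average. With 150 events, that is 10 to 25 events per site. A 100-patient site would have about 7 events and, at 10-15%, 10-15 INT patients.

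**3. Confounding by site (illustration).** The documents give no between-site figures, so these inputs are assumed: half the patients are at sites referring 5% to INT and half at sites referring 20% (mean 12.5%, inside the plan's 10-15%); the event rate at high-referral relative to low-referral sites is r; INT has no effect.

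- Share of INT patients from high-referral sites: 0.20/(0.20 + 0.05) = 0.80.
- Share of MED patients from high-referral sites: 0.80/(0.80 + 0.95) = 0.457.
- Apparent ratio = (0.80r + 0.20)/(0.457r + 0.543).
- r = 0.67: 0.736/0.849 = 0.87. r = 2.0: 1.80/1.457 = 1.24.

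As a check, 300 simulated cohorts of 2,200 at 10 sites with about 155 events gave mean ratios of about 0.86 and 1.20 without site, and 0.99 and 0.98 with site. The simulated means lie slightly below the closed form because the mean log ratio has a small-sample bias. Adding site raised the standard error by less than 0.01, from a base of about 0.25.

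**4. Intervals on event rates.** Statistical Analyses, Specific aim 1 reports rates by ischemia status, so the cluster is the ischemic or non-ischemic part of a site. Sample Size gives 23% ischemia. With m patients per cluster, the interval is too narrow by √[1 + (m − 1) × ICC]. The ICC of 0.002-0.01 is assumed.

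| Stratum | m (15 to 6 sites) | 15 sites, ICC 0.002 | 6 sites, ICC 0.01 |
|---|---|---|---|
| Ischemia | 34 to 84 | √1.065 = 1.03 | √1.833 = 1.35 |
| No ischemia | 113 to 282 | √1.224 = 1.11 | √3.813 = 1.95 |

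**5. Cost of adjusting.** If exposure shares R² of its variance with site and year, effective events are multiplied by (1 − R²). In step 3, R² = 0.075²/(0.125 × 0.875) = 0.05, which takes power at HR 0.59 with 160 events from 80.2% to 78.1%. At an assumed R² of 0.20 it is 71.0%. These figures use the plan's 77:23 split. With 10-15% INT and 150 events, power at that HR starts lower, at 49-64%.

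Site dummies (5-14 df) plus year dummies (4-5 df) on top of the plan's 10 variables make 19-29 df. That leaves 150/19 = 7.9 down to 150/29 = 5.2 events per df, against the plan's 15. Stratifying by site with one year term makes 11 terms, or 150/11 = 13.6.

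**The case against.** The strongest reply is that the plan does not shut site out. The Aim 1 covariates are examples, the propensity model may consider anything that affects referral, and the score is itself entered in Step 2. A site term in the score would therefore reach the Aim 2 Cox model. This stands. A reader might infer that site is excluded, or that the Step 2 list is closed, but the text supports neither. What remains is that a bias the plan names has no analytic remedy, and the choice is left until outcomes may have been seen.

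The size is also open to challenge. The illustration omits the planned score, % ischemia, age, sex and diabetes, which may absorb part of any site difference. On the log scale its extremes (−0.14 to +0.21) are smaller than one standard error of about 0.25. This too stands: it shows what is possible, not the bias expected in this study. No corresponding bias is shown for scan year or for the ischemia hazard ratio in Aim 1.

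A reader might apply the design effect to whole sites of 147-367 patients and obtain factors up to 2.2. The planned rates are stratified by ischemia, so the smaller clusters in step 4 apply. Nor should that design effect be carried over to hazard ratios, because exposure varies within sites. Finally, nothing in the documents shows that outcome capture differs between sites; Sample Size assumes 4-year follow-up for everyone.

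**Conclusion.** The omission is certain from the text; its size is not. The Aim 2 INT versus MED comparison is where it matters most. There, site differences in both referral and event risk could move a null effect to an HR of about 0.87-1.24 before other adjustment, on the assumed inputs. Intervals for stratum-specific event rates would be too narrow by 1.03-1.35 (ischemia) or 1.11-1.95 (no ischemia) on an assumed ICC, and the top of each range needs both the highest ICC and only six sites. It would be too strong to say that the planned analysis is biased by these amounts, or that adjusting costs nothing. The change should be made because the plan already identifies the problem and the remedy is simple.

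**What to change.** In the SAP:

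- Stratify the Cox models for sub-aims 2.1 and 2.2 by site. Do the same in Aim 1 for consistency.
- Name site and a low-df scan-year term (for example linear) as mandatory in the propensity model. With about 300 INT patients, the six named predictors plus site and even categorical year use 15-25 df, or 20 down to 12 INT patients per df.
- Give site-clustered intervals for annualized event rates, with a small-sample correction because there are only 6-15 clusters.
- Avoid full site and year dummies in the Cox models, and strict within-site matching, which may lose pairs at small sites.
- Reconcile the scan window, which sets the range of the year term: "underwent stress CMR perfusion imaging for evaluation of myocardial ischemia between 2008-2013" in Study Cohort and Enrollment Criteria against "stress CMR studies performed between 2008-2012" in Bias considerations.

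The cost is wording. Site and scan date must already be known in order to apply the per-site limits and the date search. Precision falls a little when treatment overlaps modestly with site, and more when the overlap is strong (about 80% to 71% power at R² = 0.20). The 150-160 events behind these figures are deaths and AMI only; the primary outcome also counts late revascularization, so the events available should be more numerous.

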## **Statistical Analyses**

### **Specific aim 1**

Unadjusted and multivariable survival analyses associating presence of ischemia and percent ischemic myocardium (both by CMR), with the primary and secondary clinical outcomes will be performed. In the multi-variable analyses, key known risk markers such as age, patient sex, left ventricular and systolic volume (LVESV), validated pretest coronary disease probability, and validated risk score (Diamond and Forrester) will be modeled, and then extent of ischemia by stress CMR studies will be added to the model to test the null hypothesis that CMR findings do not add predictive value, versus the alternative hypothesis that stress CMR findings do add predictive value. A significance level of 0.05 will be used. Since CMR findings will affect patient management, which in turn, will affect the clinical outcomes, in a secondary analysis, cardiac treatment (e.g. revascularization) received within 60 days of the CMR will be added to the above model to account for treatment effects on the relationship between extent of ischemia and outcome. Annualized event rates of the primary and secondary outcomes, stratified by CMR ischemia (present or absent), and CMR ischemic burden (mild, moderate, high), will be determined, both unadjusted and adjusted for cardiac treatments received. We also plan to calculate net reclassification index of these CMR metrics to event-free survival (primary and secondary outcomes). In addition, we will examine the annual event rates of primary and secondary outcomes in each of these subgroups and perform corresponding comparative analyses.

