### Specific Aim 1 – Association of CMR ischemic burden with clinical outcomes in the real-world

To test the hypothesis that stress CMR perfusion imaging adds predictive stratification of clinical outcomes over known risk factors for patients presenting with chest pain syndromes, at moderate pre-test risk, in a multicenter real-world setting in the US. Endpoints of interests include both primary and secondary outcomes. This aim is important because it provides the prognostic association of key CMR variables of ischemia with the observed primary and secondary events without and with adjustments to known clinical markers of patient risks, annualized event rates of primary and secondary outcomes either annualized across the entire study period or at specific intervals of study follow-up (e.g. first, second, third year of follow-up etc), net reclassification index by CMR metrics of ischemia towards current guideline-supported treatments, and potential alteration of diagnostic and therapeutic thinking.

Specific aim 1 will assess the prognostic association of presence of ischemia and percent ischemic myocardium (both by CMR) with the primary and secondary clinical outcomes. In the multi-variable analyses, key known risk markers such as patient age, patient sex, left ventricular and systolic volume (LVESV), validated pretest coronary disease probability, and validated risk score (Diamond and Forrester) will be considered for inclusion in a multivariable model, and then presence or extent of ischemia by stress CMR will be added to the model to test the null hypothesis that CMR assessment of ischemia do not add prognostic value, versus the alternative hypothesis that stress CMR assessment of ischemia do add predictive value. A significance level of 0.05 will be used. Since CMR findings will affect patient management, which in turn, will affect the clinical outcomes, in a secondary analysis, cardiac treatment (e.g. revascularization) received within 60 days of the CMR will be added to the above model to account for treatment effects on the relationship between extent of ischemia and outcome. Annualized event rates of the primary and secondary outcomes, stratified by CMR ischemia (present or absent), and CMR ischemic burden (mild, moderate, high), will be determined, both unadjusted and adjusted for cardiac treatments received. We also plan to calculate net reclassification index of these CMR metrics to event-free survival (primary and secondary outcomes).

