## Sample Size

### For sub-aim 1:

The rate of cardiac hard events (death and acute MI) is estimated based on reported evidence of 0.5% and 6% per year for patients who have absence and presence of ischemia on CMR perfusion imaging, respectively. We plan to collect follow-up events for a 4-year period after CMR. Based on prior evidence, prevalence of ischemia on CMR perfusion was 23% in referred patients.

With a sample size of 2,200 patients, 506 (23%) are assumed to be with presence of ischemia and 1694 (77%) with absence of ischemia. With incidences of 6% and 0.5% per year and a 4-year follow-up, a total of 124 of 506 patients with ischemia and 36 of 1694 patients with no ischemia are expected to experience an event, i.e. a total of 150 patients with event.

A sample size of 2,200 patients overall and 150 patients with event in a 4-year follow-up is regarded sufficient to run multivariable analysis with up to 10 variables.

With regards to the sample size considerations on the time-to-event analysis, the following settings and assumptions were used:

- Power = 80%
- Level of significance (two-sided) = 5%
- Assumed proportion in control group (i.e. no revascularization) = 77%
- Total sample size = 2,200 patients
- Number of events = 150 in total sample
- 4-year follow-up for all patients available
- The hazard ratio is estimated by a Cox proportional hazard model

With a sample size of 2,200 patients and an event rate of 124 in group 1 and 36 in group 2, a hazard ratio of 0.59 can be detected with the above mentioned settings and assumptions (i.e. 41% risk reduction rate).

For sub-aim 2.3 (comparison to the historical FAME 2 study

As reported in published data (own BWH dataset and [name] et al Circulation 2011 Apr 12;123(14):1509-18), the event rate of patients who underwent revascularization guided by CMR ischemia (i.e. CMR physiologic guidance) is about 5% per year, i.e. 10% in a 2-year follow-up. In the

historic fame-2 study, the 2-year event rate of patients who did not use physiological guidance (N=441), was 19.5%. With a power of 80%, a two-sided alpha of 5% and an assumed difference under H1 of -9.5%, the sample size of patients in this registry needs to be at least 180 patients.

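### Aim 2 adjusts for ischemia only through percent ischemic myocardium, although 77% of patients are expected at zero; without a presence term the INT versus MED comparison can be biased against INT, and an Aim 1 extent slope alone cannot show burden beyond presence

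*Combined protocol and SAP*

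**What the plan says.** **Aim 1.** The aims section says: "then presence or extent of ischemia by stress CMR will be added to the model". The Statistical Analyses section, Specific aim 1, says: "then extent of ischemia by stress CMR studies will be added to the model to test the null hypothesis". In both places the null is that CMR ischemia adds no prognostic or predictive value. The analysis section also plans survival analyses of presence and of percent ischemic myocardium. It adds annualized event rates by present/absent and by burden band, with comparisons between these subgroups.

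**Aim 2.** Step 1 lists likely predictors of referral for the propensity model; its ischemia measure is "ischemic myocardium (% myocardial mass based on number of segments, by CMR". Step 2 says: "Key known risk markers to be included in these models are age, sex, diabetes, and % ischemic myocardium". Neither step names presence of ischemia. Step 2 then enters treatment and the propensity score into the Cox model.

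**Distribution and rates.** The Sample Size section, For sub-aim 1, says "prevalence of ischemia on CMR perfusion was 23% in referred patients" and therefore "506 (23%) are assumed to be with presence of ischemia and 1694 (77%) with absence of ischemia". Its hard-event rates are 0.5% per year without ischemia and 6% with it. It gives no rate by extent.

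**Silence.** No section says whether extent enters as a line, a spline, bands, or together with a presence term. The checks planned for Aim 2 are proportional hazards, the treatment association with and without matching, and a comparison of key risk markers between the treatment groups.

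**The concern.** A variable that is zero for about three quarters of the cohort and positive for the rest carries two pieces of information: whether there is any ischemia, and how much. One slope has to serve for both. If risk rises sharply between none and any, a straight line gives patients with mild ischemia too little of that rise.

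In Aim 2 this matters because ischemia is the main reason for referral to INT. If referral also rises sharply at presence, INT patients carry risk that neither the score nor the Cox covariate removes. The remaining confounding makes INT look worse than it is, which could hide the benefit that sub-aims 2.1 and 2.2 are meant to test.

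In Aim 1 the stakes are smaller. The aim's title speaks of ischemic burden, but a significant extent slope can come entirely from the contrast of none with any. In addition, the two Aim 1 sections do not name the same test variable.

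**Working it through.** **1. Inputs from the documents.** N = 2,200; 506 with and 1,694 without ischemia; 0.5% and 6% per year (ratio 6/0.5 = 12); 4 years of follow-up; two-sided 5% level; 80% power; INT in 10–15% of patients.

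**2. The plan's own figure.** Schoenfeld: HR = exp[−(1.960 + 0.842)/√(D × 0.23 × 0.77)]. With D = 124 + 36 = 160, HR = exp(−2.802/5.323) = 0.59, as stated. With the stated total D = 150, HR = 0.58. The split is labelled "Assumed proportion in control group (i.e. no revascularization) = 77" percent, but 77% is the ischemia-free share; Specific aim 2 expects 85–90% on MED. That is a separate matter. I use 0.59 below only as an example of a real benefit.

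**3. Why one slope falls short of a step.** Suppose hazard is 12 times higher at any extent. A single linear term fitted to such data gave HR 1.21–1.23 per segment. A patient with 3 ischemic segments is then credited with 1.21³ = 1.77 to 1.23³ = 1.86 times the hazard of a patient with none, not 12. The line reaches 12 only at ln 12/ln 1.23 = 12.0 to ln 12/ln 1.21 = 13.0 of the 17 segments.

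**4. Aim 2 simulation, main set.** Assumptions not in the documents: mild/moderate/severe split 55/30/15% or 34/33/33% among ischemic patients; referral by extent; one prognostic and one referral-only covariate. There were 200 runs per setting, with an INT share of 8–13%. Results for the 34/33/33% split with true INT HR 1.00 (rejection rate in brackets):

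| Risk | Referral | Linear extent + score as covariate | Presence + extent | 1:1 matched on linear score |
|---|---|---|---|---|
| step | step | 1.69 (76%) | 0.98 (3%) | 1.07 |
| step | graded, with a jump at zero | 1.42 (39%) | 0.99 (6%) | 1.04 |
| step + gradient | step | 1.42 (43%) | 1.02 (4%) | 1.05 |
| step + gradient | graded, with a jump at zero | 1.28 (24%) | 1.00 (3%) | 1.02 |
| step | linear on logit | 0.99 (9%) | 0.99 (6%) | 0.98 |
| log-linear | step | 1.00 (2%) | 1.01 (4%) | 1.03 |

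Over both splits, when risk and referral both jump at zero:
- True HR 1.00: the linear term gives 1.28–1.94 (24–86% rejection). Presence plus extent gives 0.97–1.04 (3–8%). With 200 runs, 5% has a Monte Carlo standard error of √(0.05 × 0.95/200) = 1.5 points, so 3–8% is compatible with 5%.
- True HR 0.59: the linear term gives 0.69–1.04 (9–35% rejection). Presence plus extent gives 0.56–0.60 (57–77%).
- Matching on the linear score gives 1.02–1.11 for a true 1.00 and 0.59–0.66 for a true 0.59. In the first row of the table, 87% of matched INT patients but 80% of matched MED patients had ischemia.

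**5. Aim 2 under other assumptions (true HR 1.00).**
- Segments even over 1–10; INT in 54% of ischemic and 0.5–2% of other patients. The INT share is (273 + 8)/2,200 = 12.8% to (273 + 34)/2,200 = 14.0%, inside the plan's range. Score as covariate: 1.15–1.20 (14–17%). Presence plus extent: 1.00–1.01 (4–6%).
- The same, with INT in 1% of others and only extent in the score (150 runs). Covariate: 1.17 (13%). Matched: 1.00 (3%). Adjusting by none/mild/moderate/severe: 1.00 (4%). With referral rising by extent, the covariate result falls to 1.04–1.08 (7–9%).
- A further set with steps in both, including settings where both also rise with extent. Covariate: 1.3–2.3 (26–95%). Matched: 1.2–1.5. Presence plus extent: 0.99–1.03 (5–8%).

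**6. Aim 1.**
- No ischemia effect at all (1,000 runs): the single term rejects in 4.2%.
- Step at presence and no gradient beyond it: the single term is significant in 100% of runs, with HR per segment 1.21–1.23 (1.28 with segments even over 1–10). With presence in the model, extent is significant in 3–6%.
- True gradient of HR 1.10 per segment: extent given presence keeps 83% power.

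**The case against.** **A reader might infer that Aim 1 will report a dose-response that does not exist.** The documents do not support this. Neither Aim 1 section states a dose-response hypothesis. When presence matters, rejecting the null of no added value is correct, and the single term holds its 5% level for that null. The plan also analyses presence and compares event rates by burden band, so a flat risk beyond presence could be seen there. What remains is that no test of extent given presence is specified. The mild band, set at 3 segments or fewer, has no stated lower bound, so zero is not expressly excluded from it.

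**A reader might infer that the plan fixes a linear term.** It does not; the form is unstated. A banded or spline term could remove most of the problem, but nothing in the plan requires either.

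**A reader might infer that the Aim 2 estimate is certainly biased.** It is not. Both risk and referral must step up at presence. The plan's two rates are averages for absent and present, and they do not rule out a gradient that starts from zero.

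**The plan names matching, and matching mostly protects.** The aims section does call for propensity matching, while Steps 1 and 2 put the score into the Cox model. Matching on the linear score reduced the bias in every set, to nothing in one, but left up to 1.5 in another.

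**The predictor list is open.** Step 1 allows other factors, so presence could be added, and the planned comparison of risk markers might reveal an imbalance. Presence is not named for either purpose, and the Step 2 covariate list does not include it.

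**Conclusion.** The concern holds for Aim 2 in conditional form. The plan names percent ischemic myocardium as the sole ischemia adjustment, expects 77% of patients at zero, and bases its event rates on absence versus presence. If the variable enters as one linear term and both risk and referral step up at presence, the hazard ratio is pushed against INT. For a true 1.00, the simulated estimates are about 1.15–2.3 with the score as a covariate and 1.0–1.5 with 1:1 matching. A true 0.59 was estimated as 0.69–1.04 in the main set with the score as a covariate.

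The direction is consistent under those conditions. The size is not, because it depends on the segment distribution and the referral pattern, which the documents do not give. There is no material bias if log-hazard or referral is truly linear in extent.

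For Aim 1, the single-term test is valid for its stated null. It cannot by itself support a statement that burden matters beyond presence, and the two sections must be made to name the same test variable.

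**What to change.** - **Propensity model and Step 2 Cox models:** enter presence of ischemia (0/1) and extent (zero if none) together, and state the scale of extent.
- **Balance comparison in Specific aim 2:** add presence of ischemia to the markers compared with and without matching.
- **Aim 1:** make the aims section and the analysis section agree. Use the joint 2-df likelihood-ratio test of presence plus extent as the test of added value. Base any statement about burden on the 1-df test of extent given presence.

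Bands with zero as their own category, or a spline with a zero indicator, would also be acceptable if fixed in advance.

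The cost is SAP wording, one extra degree of freedom per model and somewhat wider intervals. Counting each named variable as one term, Aim 1 has 5 risk markers + 2 = 7 terms, and Step 2 has 4 markers + presence + treatment + score = 7. Both are inside the 10 variables that the sample-size section regards as supportable.
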